5.2 Secondary Objectives

- To replicate selected metabolomic breath biomarker panels of acute breathlessness using a combination of both (i) discovery technologies (including GC-MS) and (ii) point of care auto tuned breath sensing devices (including linear IMS, CMS, PTR-MS).
- To evaluate the primary endpoint stratified by breathlessness as follows (i) change in eMRC by 1
 unit, (ii) patient defined breathlessness and (iii) 100 mm visual analogue score for breathlessness
- To discover and replicate metabolomic breath biomarkers that differentiate (i) Acute Heart failure,
 (ii) Community acquired pneumonia, (iii) Adult exacerbations of asthma and COPD
- To quantify the level of clinical uncertainty in the primary diagnosis using a 100 mm visual analogue scale and independent clinical adjudication of case notes blinded to the following blood biomarkers (i) CRP (ii) blood eosinophils (iii) BNP (iv) Troponin-I but not clinical history and chest X-ray.
- To identify and discover metabolomic breath biomarkers of acute childhood wheeze and or confimed asthma.

To clinically validate metabolomic breath biomarkers generated above using a combination of existing pathology markers e.g. BNP, CRP, blood eosinophils and troponin- I and other clinical relevant prognostic scoring tools e.g DECAF, CURB65 and Heart failure risk calculator http://www.heartfailurerisk.org/^[19]

- Replication of acute breathlessness biomarkers will be according to the following predefined primary diagnoses in the replication phase:
 - (i) Acute Heart failure (n=55-100),(ii) Community acquired pneumonia (n=55-100), (iii) adult exacerbations of asthma and COPD (n=110-200),(iv) paediatric exacerbations of acute childhood wheeze and confirmed asthma (n=25-100),(v) age/home environment matched adult/spouse/sibling/parent control subjects (n=55-75 adults/25 children)
 - 5.3 Exploratory End Points (where applicable)
 - 1) To evaluate the dynamic profile of breath biomarkers during (i) the acute state, (ii) in the recovery state post exacerbation.

Page 15 of 46

- 2) To evaluate the relationship between breath metabolomic biomarkers and health status/ functional measures:
- Health status measures
- Physical performance
 - 3) To evaluate the relationship between metabolomic breath biomarkers and clinical outcomes including (i) hospital readmission at time points up to 2 years (ii) response to standard clinical therapy and (iii) death.
 - 4) To explore and develop breath metabolomic biomarkers of multi-morbidity
 - 5) To evaluate the relationship between diet, lifestyle and environment upon breath metabolomic biomarkers.

To generate a biobank of DNA, RNA, urine, plasma, serum and sputum samples for future breathomic and other 'omic molecular pathology studies (including proteomic, transcriptomic, genomic and metabalomic studies).

6 STUDY DESIGN

6.1 Summary of Trial Design

The clinical study will be a prospective observational study across two acute clinical sites that routinely assess and treat cardio-respiratory admissions due to breathlessness within Leicester.

- (i) Glenfield Hospital (GGH): Adult cardio-respiratory presentations to Glenfield Hospital (including Clinical Decisions Unit (CDU) & inpatient wards), outpatient clinics and NIHR Leicester Biomedical Research Centre (BRC)
- (ii) Leicester Royal Infirmary: Adult and paediatric cardio-respiratory presentations to A&E, Children's Assessment Unit (CAU), Diagnostics Development Unit (DDU), inpatient wards, outpatient clinics and Research Space

Follow up and stable state controls will be assessed in the outpatient setting within University Hospitals of Leicester including the BRC. The study flow is summarised in Figure 1 below.

[figure not shown]

Fig 1: Study flow chart. Figure demonstrates the patient journey from admission through to outcome. Assessments carried out at

Figure 1: Study Flow chart

Prospective participants with self reported acute breathlessness, either requiring admission or a change in baseline treatment, presenting within UHL. The streaming and care pathways at UHL allocate ambulance admissions to the two units described above with appropriate clinical care being provided at each site according to national guidelines and local protocols / policies.

Patients with confirmed acute airwary exacerbation or heart failure decompensation as part of other research studies at the NIHR Leicester BRC may also be included.

Age- and/or home environment matched adult/spousal/parent and sibling healthy volunteers will be recruited where possible on the admissions unit and when not possible in the research units across both sites at a separate visit. All attempts will be made to sample breath on at least two of the same time points as patients within these disease groups, however sampling may occur in a different location and at different serial time points. All healthy volunteers will complete a range of questionnaires adapted from generic cohort studies to characterise their diet, lifestyle and environmental exposures. A stable state control population will also be recruited to compare with the unstable state. This will consist of participants with a confirmed diagnosis matched with the acute care population but not in the exacerbation state.

Specifically after triage and senior clinical assessment at each of the acute EMBER sites (CDU, DDU, CAU) if a primary clinical diagnosis of (i) exacerbation of heart failure, ii) exacerbation of asthma/COPD, (iii) adult community acquired pneumonia or (iv) paediatric exacerbations of acute childhood wheeze and confirmed asthma has been made, members of the EMBER research team will evaluate patients using breath diagnosis and sensing technologies and additional tools to characterise patients that are acutely unwell.

The following steps will be employed at all sites:

- 1) Identify patients with acute breathlessness defined as one or more of (i) patient defined acute breathlessness and/or a (ii) 1 unit increase in (eMRC)
 - 2) Completeion of study diagnosis at the point of senior clinical decision maker review
 - 3) Informed consent

Page 17 of 46

- 4) In selected patients that have not been captured during their acute admission and have been discharged prior to EMBER assessments (for example patients that may have been discharged rapidly due to the use of an ambulatory care pathway), *recall within 48 hours of discharge* will be performed for EMBER assessments
- 5) Breath sampling using a standardised CE marked multi-platform breath sampling face mask as well as real time breath sampling.
- 6) Collection of additional biomarkers for future biomarker discovery campaigns Including a (i) urine sample, (ii) blood sample (up to 85 mls) (DNA, RNA ,plasma and serum), peripheral blood cell flow cytometry and (iii) spontaneous sputum samples (plugs and supernatants). These samples will be collected at time point 1a/1b and at 2
- 1) Stable state follow up of all patients will occur following recovery from the acute event. Assessment will occur at time of clinical follow up, or as a separate research visit.

The expected duration of participants within the study will therefore be equivalent to their length of hospital stay and up to the stable state follow up visit, with a similar duration for healthy volunteers and stable state patients.

Readmission to hospital within the protocol defined recovery period. Patients that re admit to hospital between visits 1 and 2, can have additional $1a\pm1b$ assessments. Visit 2 will be taken as recovery following the subsequent admission. If a patient is admitted to hospital after visit 2 then they will be eligible to be recruited as a new study participant.

Definition of Acute Breatlessness

A standard definition for acute breathlessness does not exist. We will use the presence of patient reported acute breathlessness, above their usual baseline breathlessness (i.e. in stable state) as a binary variable. We will also use the extended MRC score, and 100mm visual analogue score (VAS), as a continuous variable.

The extended MRC score has been validated in chronic disease populations, including in the acute state, and may be applied to diseases other than COPD where originaly validated. We will define a change in breathlessness of the eMRC as at least a unit change from stable state. In addition a VAS score will be used to measure breathlessness.

Definition of Post Exacerbation Recovery

Patient recovery will be defined as

- (i) Patient reported recovery from the acute exacerbation spell and back to their baseline extended MRC score or clinician defined recovery from the acute exacerbation spell and
- (ii) At least 6 weeks post exacerbation event (up to 6 months).
 - 6.2 Summary of Additional Assessment and breath sampling procedures/ devices

A number of analytical devices will be utilised to sample breath in acutely ill patients and based upon the (i) clinical site, (ii) operational needs and likely patient grouping (severity of underlying condition at the point of admission) within each clinical site, (iii) balance of discovery and point of care sensing technologies: breath sensors will be co-located to the two EMBER acute admissions units. All devices will be maintained to a high level of operational readiness by the technicians and device specialists within the clinical operations group. All devices will be checked for safety by Medical Physics at University Hospitals of Leicester NHS Trust.

[figure not shown]
The following devices will be utilised to evaluate breath volatile organic compounds

Page 18 of 46

- A portable mass spectroscopy device (Advion Ltd) for discovery based metabolomic breath sampling. This device is also capable of real time sampling.
- A proton transfer mass spectroscopy device (PTRMS) for discovery based metabolomic breath sampling.
- A point of care GC-FAIMS Lonestar device (Owlstone Nanotech Ltd)
- A point of care linear IMS Bioscout device (Owlstone Ltd: GC-FAIMS Lonestar analyser)

A CE marked breath sampling device developed by Owlstone Nanotech Ltd (Appendix A) will be used to sample breath in the majority of patients onto adsorbent Tenax tubes as well as acquiring online sampling. This effectively allows de coupling of the breath sampling from the breath sensor and analysis platforms in selected patients and allows patients that are not able to be mobilised in a chair to a real time breath sampling device to be sampled at their bedside. The Owlstone RECIVA sampler (Figure 3) is capable of entraining oxygen and is therefore suitable for patients in respiratory failure requiring low to moderate flow rates of oxygen to maintain target oxygen saturations. CE marking approvals are appended to this protocol in (Appendix B).

Figure 2: Owlstone CE Marked Breath Sampler

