2. SYNOPSIS

Trial Design Pr	onsor Reference 0569 ospective Acute Care 'Real Life' Observational Study
Trial Participants Pa	
со	tients with acute breathlessness in the following (post-acute pathway nfirmed) strata:
1 * *	Acute Heart failure , characterised by a clinician diagnosis, and a proto-typical sponse to treatment.
re	Community acquired pneumonia , defined as new radiological consolidation sponsive to treatment according to the British Thoracic Society (BTS) mmunity acquired pneumonia guidelines.
wi pr) Adult exacerbations of asthma and COPD, defined as a clinician diagnosis th objective confirmatory evidence of disease based upon historical or ospective measurements, requiring an acute change in treatment (e.g. tibiotics, oral corticosteroids or increased bronchodilator therapy)
(iv) Paediatric exacerbations of acute childhood wheeze and or confirmed asthma
he an wi	Age and/or Home environment matched Adult/Sibling/Parent/Spousal althy volunteers, who have no prior history of asthma, COPD, heart failure d have not been admitted to hospital with community acquired pneumonia thin 6 weeks of the baseline study visit. Additional healthy volunteers will also recruited from local databses.
as) Stable state aged matched participants with a confirmed diagnosis of thma, COPD or heart failure, that have not had and exacerbation of their sease within the preceding 6 weeks.
Planned Sample Size Ar	interim analysis was conducted in September 2017 to determine the sample
siz	e of the ember acute study. Guided by literature search, a panel of 10 pre
sp	ecified aldehyde biomarkers derived from GCMS analysis were supplied. The
bio	omarkers were normalised to a common standard and were not background
su	btracted.
A	closed formula from Hsieh et al, Statis med 1998, was utilised to calculate
sa	mple sizes from logistic regression models of the 10 aldehydes with acute
br	eathlessness as the outcome measure. The sample size estimates are also
re	evant to acute class comparisons vs. the sum of other acute classes.
Ва	sed upon the samples size estimates we would have an 80% power at the 5

	% significance level to detect an odds ratio of association of 1.2 for a given
	disease class with minimum of 55 patients per disease class.

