The proposed program of research will identify and evaluate the diagnostic and prognostic value of exhaled breath metabolomic biomarkers in acute cardio respiratory breathlessness and common indicator diagnoses associated with acute cardio respiratory breathlessness. Specific indicator conditions have been selected according to their (i) relatively high prevalence, (ii) high unmet need, mortality and morbidity and (iii) need to develop better diagnostic and prognostic algorithms in acute care pathways.

The focus of the research program will be to phenotype using a combination of 'discovery' and near-patient care breath sampling technologies in acutely breathless patients attending two acute admissions units within Leicestershire. The indicator diagnoses of interest are (i) acute heart failure, (ii) exacerbations of adult asthma and COPD, (iii) community acquired pneumonia and (iv) paediatric exacerbations of acute childhood wheeze and confirmed asthma. Other disorders that are associated with acute breathlessness including exacerbations and acute presentations of pulmonary fibrosis, acute pulmonary embolism will not be studied within the program due to low prevalence, lack of standardised definitions and likely small sample size (pulmonary fibrosis) and adequate acute companion diagnostics (pulmonary embolism).

The program will be divided into two phases. **Phase 1**, a discovery phase to identify putative breath biomarker panels and **phase 2**, a validation phase to replicate and validate selected biomarkers within phase 1 using point of care breath sensing devices.

Patient level clinic-pathological and outcome data (spanning the entire acute pathway) will be collected in parallel to breath sampling. In addition, breath samples will be acquired during the recovery from the acute state and in the stable state post exacerbation to better understand the kinetics of breath analytes associated with these diseases.

A parallel cohort of age/home environment matched Adult/ parent/sibling/spousal healthy volunteers will also be recruited and evaluated at selected matching time points with breath analysis and a range of questionnaires to evaluate factors that are known to influence the metabolome including diet, lifestyle and the environment. Additionally patients with stable asthma, COPD and heart failure will be recruited from primary and secondary care as disease control populations.

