7.3 Exclusion Criteria

The participant may not enter the study if ANY of the following apply:

Page 20 of 46

- Female participants who are known to be pregnant, lactating or planning pregnancy during the course of the study.
- (ii) Current participation in a clinical trial of an investigative medicinal product or within 3 months or 5.5 half-lives of the IMP whichever is longer.
- (iii) Active or clinically suspected pulmonary tuberculosis
- (iv) In the opinion of the treating physician, breath sampling during the acute admission would be clinically unsafe or inappropriate due to the patient's condition or poor prognosis. Examples include malignancy or autoimmune disease with anticipated survival of under 1 year, and chronic renal replacement therapy.
- (v) Unable or unwilling to give informed consent by visit 1b.
- (vi) Any other significant disease or disorder which, in the opinion of the Investigator, may either put the participants at risk because of participation in the study, or may influence the result of the study, or the participant's ability to participate in the study.

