21.7 Stable Disease Recruitment Plan

This should be opportunistic and support the following ongoing initiatives

- Mologics COPD study
- Mepolizumab severe asthma early response study
- [name] ACF: project April 2018 (small healthy volunteer repeatability study n=12 healthy adults baseline x2, 2 weeks, 3 months GC-MS ReCIVA, PTRMS ([name] to discuss at Exec).
- Severe asthma clinical patient samples if possible/samples from aligned BRC studies (agreed at the exec)

Planned acute study recruitment last patient visit 1a

1st Nov 2018 for combined discovery and replication

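### The stable controls are described as matched to the acute patients, but the recruitment plan is opportunistic and contains nothing that delivers the matching

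*Protocol*

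**What the plan says.** The purpose of the group is comparative. Protocol section 6.1 states: "A stable state control population will also be recruited to compare with the unstable state". It then describes who they are: "This will consist of participants with a confirmed diagnosis matched with the acute care population but not in the exacerbation state". The synopsis, under Trial Participants, uses the phrase "Stable state aged matched participants with a confirmed diagnosis of" asthma, COPD or heart failure. Section 7.1(vi) sets the number at 200, 100 in each phase.

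On sources, the protocol speaks in three places:

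- Section 4 (Background and Rationale) says that these patients "will be recruited from primary and secondary care as disease control populations".
- Section 8.2 names cardiology and respiratory outpatient clinics, paediatric respiratory clinics and research databases.
- Section 21.7, the only section headed as a recruitment plan for this group, says: "This should be opportunistic and support the following ongoing initiatives". Its list includes "Mologics COPD study", "Mepolizumab severe asthma early response study", a small healthy-volunteer repeatability study, and severe-asthma clinical samples or samples from aligned studies.

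Section 7.3(ii) excludes anyone with "Current participation in a clinical trial of an investigative medicinal product or within 3 months" (or 5.5 half-lives, if longer).

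**The concern.** A matched control group is one whose composition is controlled at recruitment. An opportunistic group takes whoever other projects supply. The protocol promises the first and plans the second.

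What is at stake is the reading of any acute-versus-stable difference in breath compounds. Both asthma sources that 21.7 names specifically are severe asthma, and one is identified by a biologic. The acute asthma patients are not restricted on chronic severity or biologic use. A compound that tracks severity, a maintenance drug or age could then pass for a marker of the acute state, and a reader told that the groups were matched would have little reason to suspect it.

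Section 10 gives no protection here. The primary model in 10.1 lists age, sex, blood markers, canonical breath compounds and, where relevant, comorbidity scores, but neither chronic severity nor maintenance treatment. The secondary models allow acute risk scores and acute treatments, but they compare acute diagnoses with one another.

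**Working it through.** **Side-by-side reading.** There is no stated figure to reproduce; the finding rests on the text.

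| Property | Stated | What the recruitment text provides |
|---|---|---|
| Same diagnosis | Section 6.1 | No target per diagnosis in 21.7 or 8.2; 21.7 names no heart failure source, but 8.2 names cardiology clinics |
| Age matched | Synopsis | No age rule or age band in 21.7 or 8.2 |
| Severity or maintenance treatment | Not claimed anywhere | 21.7 names severe-asthma and mepolizumab sources; their share of the 200 is not given |

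Diagnosis can be met case by case, but nothing fixes the mix. Age matching has no mechanism at all.

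**Which analyses use the group.** In section 10.1 the primary outcome is acute breathlessness versus recovery from it, and the stable controls are not named. The secondary models compare acute diagnoses. The model for change over time uses visits 1a, 1b and 2 with random effects per patient. The exposed comparison is therefore the one announced in 6.1, for which section 10 sets out no model.

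**Illustration of size (assumptions, not document figures).** Take a compound with no acute effect that is normally distributed with equal variance in both groups. Suppose a share f of the stable group differs by s SD for reasons of severity or treatment. The mean difference is then about d = f × s (the slight widening of the variance by mixing is ignored), and the apparent odds ratio per SD is exp(d).

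Yardstick: Appendix C aims to detect an odds ratio of 1.2. Since ln(1.2) = 0.18, a mean difference of 0.18 SD is enough to imitate it.

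Chance of a significant result at two-sided 5% (10.3 gives 5%; two-sided is assumed): Φ(d/SE − 1.96) + Φ(−d/SE − 1.96), with SE = √(1/n₁ + 1/n₂).

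- Asthma only, one phase: 55 acute (section 21.5) and 33 stable, assuming the 100 split evenly over three diseases. SE = √(1/55 + 1/33) = 0.220.
- All adults, one phase: 4 × 55 = 220 acute and 100 stable. SE = √(1/220 + 1/100) = 0.121.

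| f | s (SD) | d | Apparent OR | 55 v 33 | 220 v 100 |
|---|---|---|---|---|---|
| 0.25 | 0.3 | 0.075 | 1.08 | 6% | 10% |
| 0.25 | 0.5 | 0.125 | 1.13 | 9% | 18% |
| 0.25 | 0.8 | 0.20 | 1.22 | 15% | 38% |
| 0.5 | 0.3 | 0.15 | 1.16 | 11% | 24% |
| 0.5 | 0.5 | 0.25 | 1.28 | 21% | 55% |
| 0.5 | 0.8 | 0.40 | 1.49 | 44% | 91% |
| 1 | 0.3 | 0.30 | 1.35 | 28% | 70% |
| 1 | 0.5 | 0.50 | 1.65 | 62% | 99% |
| 1 | 0.8 | 0.80 | 2.23 | 95% | >99% |

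Without confounding each entry would be 5%. The result depends almost wholly on f and s, and the protocol gives neither. In the pooled column f is a share of all stable controls, so f = 1 is an outer bound: severe-asthma sources cannot make up the whole group if COPD and heart failure are also recruited.

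**The case against.** The best defence has four parts.

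1. Section 6.1 reads most naturally as matching on diagnosis, and no section claims matching on severity or treatment. A stable patient with severe asthma does not contradict a diagnosis match. This stands. The tension is with the synopsis on age, and with the absence of anything that fixes the diagnostic mix.

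2. Section 21.7 is not an exclusive source list. Section 8.2 brings in clinics and databases, and its cardiology clinics give heart failure a source. This also stands. A reader might infer from 21.7 alone that the stable asthma group will be mainly severe or biologic-treated, or that heart failure controls cannot be found. The documents support neither; the share is simply unknown.

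3. No analysis set out in section 10 uses the group, the study calls itself exploratory, and details are deferred to a separate data analysis plan. This limits the consequence. It does not remove the point, because 6.1 gives these 200 participants a comparative purpose and an analysis plan cannot match people after they are recruited. Adjustment can be left to that plan, provided that severity, treatment and source are recorded. Section 8.3 already collects usual medication.

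4. If the mepolizumab project tests an investigational product, 7.3(ii) already bars its current and recent participants. That is so, but 21.7 then names a source that 7.3(ii) may close. The protocol does not say whether the project counts as such a trial, so it cannot be inferred that ineligible patients will enter.

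**Conclusion.** The point holds as an inconsistency in current text with a real but limited consequence. The synopsis and 6.1 describe matching on age and diagnosis; 21.7 and 8.2 contain no procedure that produces it. As written, the acute-versus-stable comparison can be confounded by age, chronic severity and maintenance treatment.

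A reader might go on to infer that the primary result is biased. It is not affected: its comparator is recovery from acute breathlessness, and the stable controls do not enter it.

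The amount of bias cannot be stated from the documents. The figures above rest on an assumed share, assumed shifts of 0.3 to 0.8 SD and, for asthma, an assumed even split of the 100 per phase. They show that the effect could range from negligible (6% against a nominal 5%) to dominant. They do not predict what this study will see. Correction is advisable, but the primary analysis does not depend on it.

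**What to change.** Reconcile the synopsis and sections 6.1, 8.2 and 21.7 in one of two ways:

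- keep the claim and give it a procedure: targets for asthma, COPD and heart failure within the existing 200, frequency matched to the acute groups on age band; or
- delete the word matched and call the group a convenience sample.

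Matching on diagnosis and age would leave severity and treatment uncontrolled, so in both cases:

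- record the source study or clinic, chronic severity and maintenance treatment for each stable participant;
- adjust acute-versus-stable comparisons for age, severity and treatment;
- report a sensitivity analysis without participants from the severe-asthma and mepolizumab sources;
- state whether the mepolizumab project counts as a trial of an investigational product, and reconcile 21.7 with 7.3(ii) accordingly.

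While doing so, align section 4, which mentions primary care, with section 8.2, which names hospital clinics and research databases.

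Cost: a wording amendment, a few recorded fields and slightly more analysis. The total stays at 200. Under the first option, some samples from aligned studies may no longer count towards it.
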